# 9.6. Time Period and Frequency of Detecting AEs and SAEs

AE/SAE will be detected and recorded from the time a subject consents to participate in the study until he or she has completed the study (including a 28-day follow-up period). All SAEs assessed as related to study participation (e.g., protocol-mandated procedures, invasive tests, or change in existing therapy) or related to a GSK concomitant medication, will be reported promptly to GSK.

The investigator will monitor all ongoing AEs/SAEs after discontinuation of study treatment until the AE/SAE is resolved or until the subject is lost to follow-up.

## 9.7. Pregnancy

A screening serum  $\beta$ -HCG pregnancy test is mandatory for all women of child-bearing potential and should be done within 2 weeks prior to the first dose of Lapatinib. Thereafter, the urine or serum pregnancy test only needs to be repeated if clinically indicated or as required by local regulation.

## 9.7.1. Time period for collecting pregnancy information

The time period for collecting pregnancy information is identical to the time period for collecting AEs, as stated in Section 9 "Time Period, and Frequency of Detecting AEs and SAEs", from first dose of study treatment to 28 days after last dose.

## 9.7.2. Action to be taken if pregnancy occurs

If a female subject becomes pregnant while participating in the study, the study treatment must be immediately terminated. The investigator will collect pregnancy information record on the appropriate form and submit it to GSK within 2 weeks of learning of a subject's pregnancy. The subject will also be followed to determine the outcome of the pregnancy. Information on the status of the mother and child will be forwarded to GSK. Generally, follow-up will be no longer than 6 to 8 weeks following the estimated delivery date. Any premature termination of the pregnancy will be reported.

While pregnancy itself is not considered to be an AE or SAE, any pregnancy complication or elective termination of a pregnancy for medical reasons will be recorded as an AE or SAE (See Section 9 AE/SAE, of the protocol for definitions and a description of follow-up).

A spontaneous abortion is always considered to be an SAE and will be reported as such. Furthermore, any SAE occurring as a result of a post-study pregnancy and is considered reasonably related to the investigational product by the investigator, will be reported to GSK as described in Section 9. While the investigator is not obligated to actively seek this information in former study participants, he or she may learn of an SAE through spontaneous reporting.

# 9.7.3. Prompt Reporting of Serious Adverse Events and Other Events to GSK

SAEs, pregnancies, and liver function abnormalities meeting pre-defined stopping criteria will be reported promptly to GSK as described in the following table once the investigator determines that the event meets the protocol definition for that event.

	Initia	al Reports	•	formation on a us Report
Type of Event	Time Frame	Documents	Time Frame	Documents
All SAEs	24 hours	"SAE" data	24 hours	Updated "SAE"
		collection tool		data collection tool
Pregnancy	2 Weeks	Pregnancy Notification Form	2 Weeks	Pregnancy Follow up Form
Liver chemistry abnormalities:				
ALT >3 × ULN and bilirubin a >2 × ULN (35% direct)	24 hours	Liver Event and Liver Imaging and/or Biopsy CRFs, if applicable	24 hours	Updated Liver Event CRF

a. bilirubin fractionation should be performed if testing is available. If testing is unavailable and a subject meets the criterion of total bilirubin >2.0 × ULN, then the event should still be promptly reported as defined

The method of detecting, recording, evaluating and follow-up of AEs and SAEs plus procedures for completing and transmitting SA reports to GSK are provided in the study procedure manual. Procedures for post-study AEs/SAEs are provided in the study procedure manual.

## 9.7.4. Regulatory Reporting requirements for SAEs

GSK has a legal responsibility to notify, as appropriate, both the local regulatory authority and other regulatory agencies about the safety of a product under clinical investigation. Prompt notification of SAEs by the investigator to the appropriate project contact for SAE receipt is essential so that legal obligations and ethical responsibilities towards the safety of other subjects are met.

The investigator, or responsible person according to local requirements, will comply with the applicable local regulatory requirements related to the reporting of SAEs to regulatory authorities, and the Institutional Review Board (IRB)/Independent Ethics Committee (IEC).

# 10. DATA MANAGEMENT

Data Management will identify and implement the most effective data acquisition and management strategy for each clinical trial protocol and deliver datasets which support the protocol objectives.

For this study subject data will be collected using GSK defined case report forms and if necessary combined with data provided from other sources (eg diary data, laboratory data) in a validated data system.

Clinical data management will be performed in accordance with applicable GSK standards and data cleaning procedures with the objective of removing errors and inconsistencies in the data which would otherwise impact on the analysis and reporting

objectives, or the credibility of the Clinical Study Report. Adverse events and concomitant medications terms will be coded using MedDRA and GSKDrug, an internal validated medication dictionary.

Original CRFs will be retained by GSK, while the investigator will retain a copy. In all cases, subject initials will not be collected nor transmitted to GSK.

# 11. DATA ANALYSIS AND STATISTICAL CONSIDERATIONS

# 11.1. Hypotheses

The purpose of this phase II trial is to reject Lapatinib from further study in this indication if it was insufficiently active, and to accept it for further study if it was active. "Activity" is defined here as tumour response according to the RECIST criteria. "Indication" is defined here as advanced breast cancer with HER-2 non-amplified primary tumours and HER-2 positive circulating tumour cells (stratum 1) or advanced breast cancer patients with HER-2 non-amplified and EGFR amplified primary tumours and EGFR positive circulating tumour cells (stratum 2). Each stratum will be analyzed separately.

The study is designed in each stratum as a two-stage three-outcome phase II trial with the following assumptions [Sargent, 2001]:

- the inactivity cut-off is chosen equal to 5%, the activity cut-off equal to 20%. Hence the hypotheses of interest are H0:  $r \le 5\%$  against HA:  $r \ge 20\%$ , where r is the response rate
- the type I error rate (α, probability of accepting an insufficiently active treatment, a false positive outcome) is set to 10%
- the type II error rate ( $\beta$ , probability of rejecting an active treatment, a false negative outcome) is set to 5%
- the probabilities of correctly rejecting an inactive treatment, or of correctly accepting an active treatment, are both set to at least 80%

# 11.2. Study Design Considerations

## 11.2.1. Sample Size Assumptions

Given no response is typically expected with an anti-HER 2 treatment in the target patient population. It is believed that 10% response rate with lapatinib monotherapy will therefore be of interest in this exploratory study. Objective response will be assessed centrally by independent reviewers. Under these assumptions, the design consists of the following decision rule in each stratum:

treat 16 eligible subjects, and

• if no response is observed, declare the drug insufficiently active

- if 4 or more responses are observed, declare the drug sufficiently active
- if 1 to 3 responses are observed, proceed to the second stage as follows:

treat up to 15 additional subjects (up to 31 subjects in total), and

- if up to 2 responses in total are observed, declare the drug insufficiently active
- if 4 or more responses in total are observed, declare the drug sufficiently active
- if 3 responses in total are observed, no final conclusion can be drawn from this study

Note that after accrual of 16 subjects, the trial can terminate as soon as 4 responses are observed.

# 11.2.2. Sample Size Sensitivity

Not applicable.

## 11.2.3. Sample Size Re-estimation

Sample size re-estimation is not planned for this study.

# 11.3. Data Analysis Considerations

# 11.3.1. Analysis Populations

## **Per Protocol Population**

The per protocol population will be defined as all subject fulfilling major entry inclusion/exclusion criteria who received at least 75 % of study drug doses up to first tumour assessment at week 12, and have at least one efficacy measurement available on the primary outcome. Subjects who progress prior to the week 12 assessment will also be included in this analysis. This population will be used for the primary objective of the study and for all efficacy analyses and summaries.

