## Subjects with an NCI CTC AE Grade 3 or 4 left ventricular systolic dysfunction or interstitial pneumonitis must be withdrawn from treatment.

The investigator should perform all the assessments as listed for the Early Withdrawal in Table 8. The reason for withdrawal from study treatment must be documented in CRF.

A follow up visit should be performed in 28 days after last dose administration.

Subjects who are prematurely discontinued from the study will be not replaced.

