#### Withdrawal

Subjects will be treated until disease progression or withdrawal from study treatment due to unacceptable toxicity, consent withdrawal or other reasons. All data up to the time of withdrawal will be included in the analyses.

Subjects who are withdrawn prematurely from study treatment, but who are not withdrawn from the study at the same time, will be included in all analyses, regardless of the duration of treatment.

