## 11.5.1. Efficacy Analyses

#### Primary Analysis-Overall Response Rate

The primary indicator of drug efficacy is the overall response rate (ORR), defined as the percentage of subjects achieving either a confirmed complete or partial tumour response. This will be based on confirmed responses from the independent assessment of best overall response. Subjects with unknown or missing response will be treated as non-responders, i.e., they will be included in the denominator when calculating the percentage.

A secondary (sensitivity) analysis of the primary endpoint will calculate the ORR based on subjects with evaluable tumour response only, i.e., the denominator will only include subjects with CR, PR, SD or PD and will not include those subjects with unknown or missing best response. Further details will be provided in the Statistical Analysis Plan.

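### The per-protocol primary population conflicts with the missing-response and withdrawal rules in Section 11.5, can inflate the ORR, and leaves unclear whom the 16/31 rule counts

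*Protocol*

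**What the plan says.** Section 11.3.1 defines the PP population as subjects who meet the major entry criteria, "received at least 75 % of study drug doses up to first tumour assessment at week 12", and have at least one efficacy measurement on the primary outcome. Subjects who progress before week 12 are also included. Its role is explicit: "This population will be used for the primary objective of the study and for all efficacy analyses and summaries". The intent-to-treat set serves only as a sensitivity check.

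Section 11.5.1, on the primary ORR, says "Subjects with unknown or missing response will be treated as non-responders" and places them in the denominator. An ORR restricted to subjects with an evaluable response is labelled a sensitivity analysis.

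The Withdrawal paragraph of Section 11.5 says that subjects who leave treatment early, but do not leave the study at the same time, "will be included in all analyses, regardless of the duration of treatment".

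Sections 6.2 and 11.2.1 write the decision rule for 16, then up to 31, treated subjects per stratum, with eligibility stated for the first 16. Section 11.4 triggers the interim once 16 eligible subjects are evaluable for response. Section 6.5 adds: "Subjects who are prematurely discontinued from the study will be not replaced".

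**The concern.** Membership of the PP set depends on what happens after the first dose, and two of its conditions collide with Section 11.5.

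- **Efficacy-measurement condition.** A subject who stops for toxicity, withdraws or dies before any scan, without documented progression, is not in the PP set. Section 11.5.1 would count her as a non-responder. Once the PP filter is applied, that rule has few subjects left to act on, and the primary analysis moves close to the evaluable-only analysis that the protocol calls a sensitivity analysis. Subjects with symptomatic deterioration and no objective progression (Section 8.3.1.3) are not plainly covered by the early-progressor exception either.
- **Dose condition.** Suppose a subject stops at week 4 and has the end-of-therapy scan in Table 8 without progression. She has had at most about 4/12 = 33% of the doses to week 12, so Section 11.3.1 excludes her. If she stays in the study, the Withdrawal paragraph includes her.

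At stake are the primary estimate, which rises when treatment failures leave the denominator, and the go/no-go decision. The final outcome turns on whether a stratum has two, three or four responses, so it must be fixed in advance which subjects are counted.

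**Working it through.** **Inputs.** From Section 11.1: inactive rate 5%, active rate 20%; type I error 10%, type II error 5%; correct rejection and correct acceptance each at least 80%. From Section 11.2.1: n1 = 16 (0 responses reject, 1–3 continue, 4 or more accept); n2 = 15 (total up to 2 reject, 3 inconclusive, 4 or more accept). The share d excluded from PP is not in the protocol; I assume 5% to 30%.

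**1. The plan's own rule.** With X ~ Bin(16, p) and Y ~ Bin(15, p):

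Reject = P(X=0) + P(X=1)·P(Y≤1) + P(X=2)·P(Y=0)

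Accept = P(X≥4) + P(X=1)·P(Y≥3) + P(X=2)·P(Y≥2) + P(X=3)·P(Y≥1)

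At p = 5%:
- Reject = 0.4401 + 0.3706 × 0.8290 + 0.1463 × 0.4633 = 0.815
- Accept = 0.0070 + 0.3706 × 0.0362 + 0.1463 × 0.1710 + 0.0359 × 0.5367 = 0.065

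At p = 20%, the same formulas give accept 0.883 and reject 0.054. Read as limits, the type I error and both 80% conditions are met. The false-negative rate is 5.4% against 5%. That small excess belongs to the rule itself and not to the PP set.

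**2. Reading A: 16 and 31 are PP counts, and only non-responders are excluded.** The PP response rate is p/(1−d). At a true all-treated rate of 5%:

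| d | PP rate | Type I error | Correct rejection |
|---|---|---|---|
| 5% | 5.26% | 7.5% | 79.5% |
| 10% | 5.56% | 8.8% | 77.2% |
| 15% | 5.88% | 10.3% | 74.6% |
| 20% | 6.25% | 12.1% | 71.7% |
| 30% | 7.14% | 17.2% | 64.3% |

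Correct rejection falls below 80% at d of about 4%. The type I error exceeds 10% at d just above 14%.

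**3. Reading B: 31 treated, no replacement, exclusion unrelated to response.** Some responders are lost too, so the response rate per treated subject is p(1−d). At p = 20%:

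| d | Correct acceptance | False-negative |
|---|---|---|
| 5% | 85.5% | 6.9% |
| 10% | 82.3% | 8.6% |
| 20% | 74.1% | 13.4% |
| 30% | 63.5% | 20.3% |

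The type I error falls, from 5.6% at d = 5% to 2.1% at d = 30%. A fixed PP set of 14 + 12 = 26 (5/31 = 16% excluded) gives acceptance 78.4% and false-negative 10.4%.

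**4. Reading C: 31 treated, no replacement, only non-responders excluded.** The boundaries are response counts, and no response is lost. Every decision and error rate stays as in step 1. Only the estimate moves: with six non-responders dropped, 4/31 = 12.9% becomes 4/25 = 16.0%.

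**The case against.** The strongest reply is that the decision rule never names the PP set. It is written on treated subjects, capped at 31 per stratum, without replacement. Under Reading C no decision changes. Reading A at d = 20% would need about 31/0.8 = 39 dosed subjects per stratum, above the cap. Early progressors are kept in PP, and an ITT sensitivity analysis is planned.

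Much of this stands. A reader might infer that the stated error rates fail. The protocol does not support that: applying 16/31 to PP subjects is an inference from the words on the primary objective, Reading C leaves every rate intact, and Readings A and B rest on an assumed share and on different assumptions about who is excluded. Two further inferences also fail:

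- A single 21-day hold, as Table 2 mentions, does not by itself remove a responder from PP. It leaves 63/84 = 75%, which meets the threshold.
- Section 11.5 does not count under-dosed subjects as non-responders. Its rule covers unknown or missing response; an under-dosed subject with a scan keeps her observed response. The Withdrawal sentence covers only those who stop treatment without leaving the study.

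What the reply does not remove is the conflict in current text. The ITT analysis is secondary by definition and cannot say which primary denominator is right. Section 11.4, which waits for evaluable subjects, gives some support to counting something other than treated subjects at stage one. Because the protocol itself states both rules, leaving detail to an analysis plan does not settle it.

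**Conclusion.** The point holds as an internal contradiction over the primary analysis set, with a possible upward bias in the ORR. The bias grows with the number of treatment failures removed and is limited by the retention of early progressors; the six-subject example, 12.9% to 16.0%, shows the scale.

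The effect on the go/no-go rule is conditional. The design's exact characteristics (type I error 6.5%, correct rejection 81.5%, correct acceptance 88.3%, false-negative 5.4%) are not guaranteed, because the text does not settle which subjects the rule counts. Depending on the reading, rejection of an inactive drug weakens (A), acceptance of an active drug weakens (B), or nothing changes except the estimate (C). All these sizes rest on an assumed excluded share. This should be corrected before any stage decision is taken.

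**What to change.** Make the primary set, for the ORR and for both stage decisions, all treated subjects who met the entry criteria. Judge this on pre-treatment facts as the protocol defines entry: local HER-2 status, the CTC rule, measurable disease and the other listed criteria. State that 16 and 31 count these subjects. Count missing, unknown or unconfirmed response as non-response.

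Do not define the primary set by central HER-2 confirmation. Section 8.1.1 rests selection on the local result and requires central testing only after registration, so this would add another post-entry exclusion. A centrally confirmed HER-2-negative subset can be a sensitivity analysis, as can the present PP set.

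Reconcile Section 11.2.1 (and its parallel in 6.2), Section 11.3.1, Section 11.4, the Withdrawal paragraph of 11.5 and Section 11.5.1. With this set, the rule has the characteristics from step 1 of the working, including the 5.4% false-negative rate. The cost is a few sentences in several sections and the matching analysis-plan text. The sample size does not change. The reported ORR may be slightly lower.

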## Intent-to-treat population

The intent-to-treat population will be defined as all subjects entered into the study. This population will be used to assess the sensitivity of the efficacy and safety analyses to protocol violations.

## Safety Population

The safety population will be defined as all subjects who received at least one dose of study drug. The safety population will be used for all demographic, background and adverse event summaries and analyses. Subjects who do not receive treatment according to assignment will be grouped according to treatment received.

### 11.3.2. Analysis Data Sets

Not applicable.

### 11.3.3. Treatment Comparisons

This is a single-arm study with all eligible subjects receiving lapatinib, so there will be no comparisons between treatments.

## 11.4. Interim Analysis

An interim analysis will be performed as soon as 16 eligible subjects can be evaluated for response. The study recruitment will continue beyond 16 subjects until tumour response can be evaluated on the first 16 subjects.

## 11.5. Key Elements of Analysis Plan

This trial will use standard methodology applicable to oncology phase II trials. Details will be provided in the Statistical Analysis Plan. The final analysis will take place once all subjects have completed the study.

#### Withdrawal

Subjects will be treated until disease progression or withdrawal from study treatment due to unacceptable toxicity, consent withdrawal or other reasons. All data up to the time of withdrawal will be included in the analyses.

Subjects who are withdrawn prematurely from study treatment, but who are not withdrawn from the study at the same time, will be included in all analyses, regardless of the duration of treatment.

#### Missing Data

As the duration of treatment for a given subject will be dependent on efficacy and toxicity of study treatment, the duration of follow-up will vary between subjects. Consequently, there will be no imputation for missing data. Details will be given in the Statistical Analysis Plan. "Sub-sections" may be included or omitted for certain types of analyses, as applicable to the study purpose. Describe the following for each endpoint supportive of primary objective(s) using the relevant "sub-headings", including any specific requirements indicated in the "sub-sections" below:

- Details of any data derivation/transformation/pooling (e.g., of study sites) to be applied, and any subgroups to be analyzed.
- Methods for handling data from subjects, who are withdrawn from the study, investigational product, or both. Procedures for analyses if study is prematurely discontinued.

- Methods for handling unused, missing, spurious, unscheduled, or repeated data. For example, if missing data are imputed using a LOCF procedure, specify the methodology to be used.
- Planned methods used to summarize or analyze the data, giving details of models fitted, hypotheses, significance levels for main effects and interactions, covariates and planned comparisons. Omit any details already addressed in previous sections.
- The way to handle any anticipated analysis problems and report deviations from the planned analysis.
- Justification of models and/or reference to methodology considered uncommon or novel.
- Any applicable assessment windows, clinical concern/threshold values, or categorizations to be applied.
- Statement of any procedures to be applied for multiple tests (e.g., multiple endpoints/time points).

## 11.5.1. Efficacy Analyses

#### Primary Analysis-Overall Response Rate

The primary indicator of drug efficacy is the overall response rate (ORR), defined as the percentage of subjects achieving either a confirmed complete or partial tumour response. This will be based on confirmed responses from the independent assessment of best overall response. Subjects with unknown or missing response will be treated as non-responders, i.e., they will be included in the denominator when calculating the percentage.

A secondary (sensitivity) analysis of the primary endpoint will calculate the ORR based on subjects with evaluable tumour response only, i.e., the denominator will only include subjects with CR, PR, SD or PD and will not include those subjects with unknown or missing best response. Further details will be provided in the Statistical Analysis Plan.

#### Secondary Analyses

The following secondary endpoints will be analysed. Tumour response and disease progression will be based on the assessments from the independent review of objective evidence (e.g., radiological scans and medical photographs).

- Clinical benefit response rate: the percentage of subjects achieving a confirmed or partial response or stable disease for ≥24 weeks.
- **Duration of response**: for the subset of subjects who show a confirmed or partial tumour response, the time from first documented evidence of CR or PR until the first documented sign of disease progression or death due to breast cancer.
- **Time to tumour progression**: the time from the start of treatment until the earliest date of disease progression or death due to breast cancer, if sooner.

• **Time to best response**: the time from the start of treatment until first documented evidence of complete or partial tumour response. When best tumour response is confirmed at a repeat assessment, the time to best response will be taken to be the time that the best response was observed.

Further details of the analysis of secondary endpoints will be addressed in the Statistical Analysis Plan.

